6.4.2 Temporary treatment interruption

Temporary treatment interruption is defined as

- Treatment taken < 80% during day 1 to the last PSG night at week 4 (inclusive) OR treatment taken on < 5 days during the last 7 days up to the last PSG night at week 4 (inclusive) for week 4.
- Treatment taken < 80% during day 1 to the last PSG night at week 12 (inclusive) OR treatment taken on < 5 days during the last 7 days up to the last PSG night at week 12 (inclusive) for week 12.

If the week 4 PSG assessment is missing, day 30 will be used instead of the last PSG night in the definition of treatment interruption for week 4 only for participants who have not prematurely discontinue treatment prior to day 30. Similarly for week 12, day 86 will be used only for participants who have not prematurely discontinue treatment prior to day 86.

The criterion for treatment taken on 5/7 days during the corresponding week prior to and including the last PSG night, as defined above, is met, if treatment has been taken for less than 5 days (i.e., at least 3 missed intakes). To calculate the number of days per week with treatment intake, a day where at least one capsule was taken, will be considered as a day with treatment intake.

To identify whether < 80% treatment was taken, compliance up to and including the last PSG night at week 4 will be calculated as

100 * Number of capsules taken up to and including the last PSG night at week 4 / (2 * study duration up to and including the last PSG night at week 4)

Compliance up to and including the last PSG night at week 12 will be calculated as

100 * Number of capsules taken up to and including the last PSG night at week 12 / (2 * study duration up to and including the last PSG night at week 12)

Study duration up to and including the last PSG night at week 4 and week 12 is derived as the number of days from the day of first study intervention intake up to and including the last PSG night at week 4 and week 12 respectively. The number of capsules taken up to and including the last PSG night at week 4 and week 12 will be calculated based on the ePRO instrument 'Study medication intake documentation'. If the 'Study medication intake documentation' on the second PSG night at week 12/EoT is missing but the last treatment intake on the eCRF 'Study intervention' pages indicate that the participant took treatment on

Version 2.0 Page: 54 of 57

the night, the 'Number of study medication capsules taken' on the 'Study medication intake documentation' will be imputed with 1 capsule.

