4.3 Justification for Dose

The clinical development program has broadly evaluated doses ranging from 1.5 mg to 300 mg. The free base form of elinzanetant in a soft gel capsule formulation was evaluated at doses between 25 mg and 160 mg once daily. A dose of 120 mg per day has been shown to be optimal with respect to efficacy on VMS, sleep disturbances, safety and receptor pharmacology.

The 120 mg once daily dose was effective on a range of measures in the SWITCH-1 study that included post-menopausal women and was more effective in improving sleep quality than the 2 lower doses studied (40 mg and 80 mg once daily). There was no relevant additional benefit from a higher dose (160 mg once daily).

The plasma concentrations achieved with the 120 mg dose are associated with full occupancy of central NK-1 receptors throughout a dose interval at steady state as demonstrated in a human PET study. Although it is not possible to assess NK-3 receptor occupancy directly, as a suitable NK-3 PET ligand does not exist, the achieved concentrations are also very likely to fully occupy central NK-3 receptors during the dose interval.

This is the first study in the clinical development program that focuses primarily on sleep disturbances associated with menopause. The same product, same dose and dosing regimen that was assessed to be effective for the VMS indication in Phase 2 studies and is currently being tested in Phase 3 studies for the VMS indication will be used to assess safety and efficacy of elinzanetant for the treatment of sleep disturbances associated with menopause.

The rationale for assessing the same dose for this second indication is based on the intention to achieve complete occupancy on both receptors and the observed effects on sleep parameters in SWITCH-1 which follow as similar dose response pattern as the effects on VMS.

For details, refer to the IB.

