6.1 Study Intervention(s) Administered

Table 6-1: Study Interventions

Arm name	Elinzanetant	Placebo	
Intervention Name	BAY 3427080 / elinzanetant	Placebo	
Type	Drug	N/A	
Dose Formulation	Soft gel capsule	Soft gel capsule	
Unit Dose Strength(s)	60 mg	N/A	
Dosage Level(s)	Two capsules daily (120 mg)	Two capsules daily	
Route of Administration	Oral	Oral	
Use	Experimental	Placebo	
Packaging and Labeling	Study Intervention will be provided in an Alu-Alu blister with 12		
	soft gel capsules. 5 blisters will be placed into 1 box containing capsules for treatment of one month. Each box will be labeled as		
	required per country requireme	nt.	
Current name	BAY 3427080	N/A	
Former Name	NT-814		

Alu = Aluminium; N/A = Not applicable.

Study intervention will be dispensed at the study visits summarized in the SoA and the first dose should be taken at home in the evening on the same day. In general, study treatment will be taken once daily before going to sleep with or without food.

If a participant forgets to take a dose in the evening, then the dose can be taken at any time up to 2 AM the same night. After this time, the dose should not be taken and will be considered a missed dose.

Returned study intervention may not be re-dispensed to a different participant.

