6.6 Dose Modification

Not applicable, all participants receiving active treatment will stay on the same dose.

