To explore the relationship between HFs and sleep disturbance as determined by PSG To explore the efficacy of elinzanetant on the frequency of anxiety symptoms To evaluate the efficacy of elinzanetant on the PGI-S and PGI-C	Frequency of HFs as measured by HFDD over time WASO as measured by PSG over time Change from baseline in GAD-7 total score over time Actual values of the PGI-C individual item scores over time Change from baseline in PGI-S individual item scores over time
Other pre-specified	item scores over time
To evaluate variability in exposure in relation to the efficacy and safety for elinzanetant	Systemic exposure of elinzanetant in plasma via sparse PK sampling
To further investigate the study intervention and similar compounds (e.g., mode-of- action-related effects, safety) and to further investigate pathomechanisms deemed relevant to sleep disturbances associated with menopause.	Various biomarkers (e.g., diagnostic, safety, pharmacodynamic, monitoring, or potentially predictive biomarkers)
To investigate the efficacy of elinzanetant on sleep disturbance associated with menopause determined by Sleepiz One+	Parameters captured remotely and continuously at home by Sleepiz One+including but not limited to e.g., WASO, TST, SE

Version 2.0 Page: 12 of 57

Estimands

The primary clinical question of interest for the primary objective is:

Does elinzanetant improve sleep disturbances associated with menopause? Specifically, what is the difference in mean change from baseline in WASO as measured by PSG at week 4 comparing elinzanetant to placebo in women with sleep disturbances associated with menopause assuming no study treatment interruption and discontinuation and no use of prohibited concomitant medications impacting sleep?

The attributes of the main estimand for the primary endpoint are as follows:

- Population: Women aged 40–65 with sleep disturbances associated with the menopause, further defined by the key inclusion/exclusion criteria.
- Variable: Change from baseline in WASO as measured by PSG at week 4.
- Treatment: Elinzanetant 120 mg or placebo.
- ICEs and strategies: Important ICEs to consider are listed in Table 1-2. (See Section 6.4 for details regarding identification of ICEs).

Table 1-2: Primary Estimand: ICEs and Strategies to Address Them

ICEs	Proposed Strategy	Data Handling Method	Interpretation

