1.2 Study Design

This is a multi-center, multi-country, double-blind, randomized, parallel-group, placebo-controlled, pilot intervention study in women with sleep disturbances associated with the menopause.

Figure 1-1: Study Schema

ICF = signing of informed consent form.

The study duration will be about 23 weeks (plus potential washout period), including:

Screening: After giving informed consent, participants will be withdrawn from prohibited concomitant medications at SCR-1 visit if needed. Screening period consists of 3 visits.

Randomization: At the end of the screening period, the participants will be randomized into elinzanetant and placebo arms in a 1:1 ratio. Randomization will be stratified by the average weekly frequency of moderate to severe HFs (including nighttime HFs) over the 14 days prior to the respective eligibility check (<35 moderate to severe HFs per week, ≥35 –<50 moderate to severe HFs per week).

Intervention period: Intervention period will last about 12 weeks:

• 120 mg (2x 60 mg soft gel capsules) of elinzanetant or matching placebo orally once daily for 12 weeks

Follow-up: The intervention period will be followed by a 4-week safety follow-up period.

The visit frequency will be once every 1–2 weeks during the screening period (depending on the scheduling of PSG) and once every 4–5 weeks during the intervention and follow-up periods.

The study includes 3 stationary visits in a sleep laboratory. Each of these visits encompasses 2 consecutive nights. This results in a total of 6 nights in the sleep laboratory.

Primary analysis will be performed after database release after LPLV.

Version 2.0 Page: 14 of 57

2. Statistical Hypothesis

The primary objective for the study is to estimate the treatment effect of elinzanetant compared to placebo in the change from baseline in WASO at week 4 as measured by PSG. No hypotheses are planned to be tested.

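### The last-7-days interruption test in SAP 6.4.2 counts nights, not capsules, so half dosing confined to the run-up to a PSG is retained in the 120 mg estimand

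*SAP*

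**What the plan says.** - **Dose.** SAP 1.2 gives "120 mg (2x 60 mg soft gel capsules) of elinzanetant or matching placebo orally once daily for 12 weeks", and Protocol 6.6 states that "all participants receiving active treatment will stay on the same dose". A one-capsule night on active treatment is therefore 60 mg.
- **Estimand.** SAP 1.1 sets "Treatment: Elinzanetant 120 mg or placebo" and handles temporary interruption by a hypothetical strategy, as if no interruption had occurred.
- **Interruption rule.** SAP 6.4.2 joins two tests by OR. The first is "Treatment taken < 80% during day 1 to the last PSG night at week 4 (inclusive) OR" the second; it divides the capsules recorded in the diary by twice the number of days. The second looks at the 7 days up to the last PSG night and is met "if treatment has been taken for less than 5 days (i.e., at least 3 missed intakes"). For that day count, "a day where at least one capsule was taken, will be considered as a day with treatment intake". The Week 12 rule has the same form.
- **Consequence.** Under SAP 4.2.2.1, data from a visit with an interruption are discarded. The section also gives a night-level example that drops a PSG night without treatment. It speaks only of treatment being taken or not and gives no capsule number.
- **Imputation.** If the diary entry for the second PSG night at Week 12/EoT is missing but the eCRF shows a dose, SAP 6.4.2 imputes one capsule.
- **Not addressed.** Protocol 9.3.1 does not define a day of treatment, and SAP 4.8 does not list the one-capsule rule among its changes.

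**The concern.** The last-7-days test is the part of the interruption rule that looks at dosing close to the PSG, and it gives the same credit for 60 mg as for 120 mg. The test that does count capsules runs from day 1, so full dosing early on can cover half dosing later.

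Two things follow. PSG values recorded after a run of half doses can enter the primary analysis as uninterrupted 120 mg. The rule can also rank women the wrong way round on recent exposure, discarding the one who took more. At stake is whether the retained data match the estimand. SAP 4.2.2.1 models discarded values on the assumption that they resemble those of participants who comply, so half-dosed women classed as compliant also enter that reference group.

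**Working it through.** **The plan's own precision figure** (used below only as a yardstick). Inputs from SAP 5: SD 33.2, 35 per arm, two-sided 90% CI, 90% probability.

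Half width = t(0.95, 68) × 33.2 × √(2/35) × √(χ²(0.90, 68)/68) = 13.23 × 1.107 = 14.65 minutes. This agrees with the stated 14.7.

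**Inputs for the rule.** Two capsules are planned per night. The last PSG night is D = 30 for Week 4 and D = 86 for Week 12, the days SAP 6.4.2 uses when a PSG is missing. D = 37 and D = 93 are my assumption for the late end of the +7-day window.

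**How many half-dose nights pass.** With full dosing and then k one-capsule nights up to and including the last PSG night, compliance is (2D − k)/(2D). It stays at or above 80% while k ≤ 0.4 × D, and the day count is 7 of 7 throughout.

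| D | Largest k | Compliance |
|---|---|---|
| 30 | 12 | 48/60 = 80.0% |
| 37 | 14 | 60/74 = 81.1% |
| 86 | 34 | 138/172 = 80.2% |
| 93 | 37 | 149/186 = 80.1% |

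**Patterns at D = 30, with full dosing before the nights described**

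| Pattern | Since day 1 | Last 7 nights | Days counted | Result |
|---|---|---|---|---|
| A: last 7 nights, none on 2, one capsule on 5 | 46 + 5 = 51/60 = 85.0% | 5/14 | 5/7 | kept |
| B: last 7 nights, none on 3, both on 4 | 46 + 8 = 54/60 = 90.0% | 8/14 | 4/7 | ICE |
| C: one capsule on each of the last 7 | 46 + 7 = 53/60 = 88.3% | 7/14 | 7/7 | kept |
| D: one capsule on each of the last 12 | 36 + 12 = 48/60 = 80.0% | 7/14 | 7/7 | kept |
| E: one capsule on each of the last 13 | 34 + 13 = 47/60 = 78.3% | 7/14 | 7/7 | ICE |
| F: one capsule every night from day 1 | 30/60 = 50.0% | 7/14 | 7/7 | ICE |

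B took more capsules than A, C or D, both overall and in the last week. B's Week 4 data are discarded and theirs are kept. E and F show where the 80% test starts to work.

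**Candidate remedies**

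- *Count a day only if both capsules were taken.* Four full nights plus three one-capsule nights is 8 + 3 = 11/14, with 4 full days: an ICE. Five full nights plus two missed nights is 10/14, with 5 full days: kept. The misranking returns.
- *ICE if fewer than 10 of 14 capsules.* A, B, C and D are all flagged, and 11/14 and 10/14 are both kept. A woman who takes both capsules or none is classified as now, since 5 nights give 10 and 4 nights give 8.
- *Half dose on the two PSG nights only.* 5 × 2 + 2 × 1 = 12/14, and 58/60 = 96.7% overall. Both remedies keep these values.
- *Imputed night.* At Week 12, four full nights plus one imputed capsule is 9/14; with both capsules on that night it would be 10/14. The imputation alone could create an ICE under the capsule test.

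**Possible dilution.** If a fraction f of elinzanetant women are affected and a fraction r of the effect remains at 60 mg, the effect shrinks by f × (1 − r). The documents give neither value. Assuming f from 2% to 10% and r from 0 to 0.75, the range is 0.02 × 0.25 = 0.5% to 0.10 × 1 = 10%. On an assumed 15-minute effect that is about 0.08 to 1.5 minutes.

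**The case against.** The strongest reply is that the ICE is an interruption, which Protocol 7.1.3 treats as a break in dosing. On that reading the day count looks for breaks and the capsule count for under-dosing. Woman B did have three nights without drug, so flagging her is correct on its own terms. This is coherent, and it stands as a possible intention. But the SAP does not state it, and it leaves under-dosing near the PSG tested only through a cumulative figure, although the estimand names 120 mg.

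Other mitigations are real but partial. The rule already tolerates two wholly missed nights in seven, so retention never meant perfect adherence. The first supplementary estimand keeps data despite interruptions, so B is retained there. ICEs are reviewed before unblinding, WASO is plotted by ICE status, and compliance is summarised. None of these isolates woman A.

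A reader might infer three stronger points that the documents do not support:

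- *That one capsule counts as full treatment throughout the rule.* It does so only in the day count. The 80% test scores such a night as half and flags half dosing from day 1, or a 13th consecutive half-dose night before day 30.
- *That the last-7-days test is the only check on dosing near the PSG.* SAP 4.2.2.1 also drops a PSG night without treatment, though it too ignores capsule number. Read alone, its example might even keep B's PSG nights, if she took treatment on them; that example and the visit-level discard need reconciling.
- *That 60 mg has been shown inferior for this endpoint.* Protocol 4.3 says the 120 mg dose "was more effective in improving sleep quality than the 2 lower doses studied (40 mg and 80 mg once daily"). It reports no 60 mg result and does not mention WASO by PSG.

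**Conclusion.** The point holds as a narrow gap in the analysis definition, of minor severity. The last-7-days test does not measure dose and the capsule test does not look at recent dosing, so half dosing limited to at most the last 12 nights at Week 4 (D = 30) or 34 at Week 12 (D = 86) is retained, and recent exposure can be ranked backwards. That does not fit a primary estimand of 120 mg without interruption.

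If 60 mg has a smaller effect than 120 mg, retaining these values biases the estimate toward no effect. The size is unknown. Even the top of the assumed range, 1.5 minutes on an assumed 15-minute effect, is small against the planned 14.7-minute half width, and the study tests no hypothesis. The documents therefore do not support a claim of material bias. The case for changing the rule is consistency with the estimand at little cost.

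**What to change.** This concerns the analysis definition only; no view is taken on dosing.

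1. In SAP 6.4.2, apply the last-7-days test in capsules: an ICE if fewer than 10 of the 14 planned capsules were taken in the 7 days up to the last PSG night, counting at most 2 per day. Use it at both Week 4 and Week 12, and align footnote a of Tables 1-2 and 4-3. Keep the 80% test.
2. Do not use a rule that counts a day only when both capsules were taken. It is not equivalent and recreates the misranking.
3. State that the Week 12/EoT night imputed with one capsule from the eCRF does not by itself trigger the ICE.
4. In SAP 4.2.2.1, define in capsules what counts as treatment taken on a PSG night. Otherwise half dosing on the two PSG nights alone (12/14) is still kept. Reconcile the night-level example with the visit-level discard.

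The cost is a few sentences and a small programming change before unblinding. Protocol 6.5 already has participants record the number of capsules each day. The downside is that a few more PSG values will be classed as ICE and handled under missing at random.

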6.5 Study Intervention Compliance

When participants self-administer study intervention(s) at home, compliance with study intervention will be assessed by site/study personnel/staff at each visit. Compliance will be assessed by review of daily diary entries and confirmatory capsule counts during the site visits and documented in the source documents and relevant form by site. Deviation(s) from the prescribed dosage regimen should be recorded.

A record of the number of capsules dispensed to and administered by each participant must be maintained and reconciled with study intervention and compliance records. An adequate record of receipt, distribution, and return/destruction of all study intervention must be captured on the dispensing log and/or in the IRT. If the participant is unable to continue taking the study intervention as required, she should contact the study site.

Study intervention capsules not returned will be considered to have been taken unless otherwise specified. At the end of the study, any remaining capsules will be collected and returned to the Sponsor, destruction depot or destroyed at the site. Any discrepancies between the returned and expected returned study interventions should be explained.

Study medication intake documenting

Participants will document the number of study medication capsules taken, together with the HFDD evening diary once daily at bedtime using the 'Study medication intake documentation' on the electronic handheld device during the treatment period as indicated in the SoA.

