4.5.1 Extent of Exposure

Treatment duration will be defined as the number of days from the day of first study intervention intake up to and including the day of last study intervention intake and will be summarized using descriptive statistics by study treatment. Treatment duration will be presented based on the data collected via the eCRF. If the date for end of exposure is not available in eCRF, the last day of intervention intake from eDiary will be used to determine the end of exposure.

The compliance (as percentage) will be calculated as:

100 * Number of capsules taken / Number of planned capsules

The number of planned tablets is calculated as:

Treatment duration * 2

All capsules, including the placebo capsules, will be counted. For participants who withdraw prematurely from the study treatment, compliance will be calculated up to the time of last dose. The compliance will be summarized descriptively by study treatment. In addition, percent of compliance will be categorized into 3 groups, <80%, 80 to 120% >120%, and the categories will be summarized by study treatment.

Version 2.0 Page: 35 of 57

Compliance will be calculated and presented twice, once based on the ePRO daily instrument 'Study medication intake documentation' and once based on the eCRF 'Drug Accountability' and 'Study Intervention' pages. If the 'Study medication intake documentation' on the second PSG night at week 12/EoT is missing but the last treatment intake on the eCRF 'Study intervention' pages indicate that the participant took treatment on the night, the 'Number of study medication capsules taken' on the 'Study medication intake documentation' will be imputed with 1 capsule.

The summaries for treatment duration and compliance will be presented for the overall intervention period, (i.e., 12 weeks).

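### A final PSG night that the eCRF accepts as treated is credited with 1 capsule against a planned 2, so diary compliance is one capsule too low for a woman who took the full dose

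*SAP*

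**What the plan says.** **Dose.** Protocol Table 6-1 (section 6.1) gives the active arm as "Two capsules daily (120 mg"), and placebo is also two capsules a day. Protocol 6.6 on dose modification reads "Not applicable, all participants receiving active treatment will stay on the same dose".

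**What the diary records.** It records a capsule count, not a yes/no on the dose: "Participants will document the number of study medication capsules taken" (Protocol 6.5).

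**Compliance for the intercurrent event.** In SAP 6.4.2 the numerator, capsules taken, "will be calculated based on the ePRO instrument 'Study medication intake documentation". The Week 12 denominator is "2 * study duration up to and including the last PSG night at week 12", so the last PSG night always adds two. One of the two criteria for temporary interruption at Week 12 is "Treatment taken < 80% during day 1 to the last PSG night at week 12 (inclusive"). The other is intake on fewer than 5 of the last 7 days, where one capsule is enough for a day to count.

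**The imputation.** If the form for the second Week 12/EoT PSG night is missing and the last intake on the eCRF shows treatment that night, SAP 6.4.2 says the count "will be imputed with 1 capsule". SAP 4.5.1 has the same rule for the exposure summary ("the 'Number of study medication capsules taken' on the 'Study medication intake documentation' will be imputed with 1 capsule"), with planned capsules defined as twice the treatment duration. Neither section gives a reason for choosing one.

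**The concern.** The rule applies only when the eCRF already indicates treatment that night. Such a night adds two planned capsules to the denominator and one to the numerator, so it is scored as a half dose. Nothing in the SAP explains this, and the study has no one-capsule regimen.

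Two outputs depend on the count. One is the diary-based compliance summary in SAP 4.5.1, including its below-80% category. The other is the below-80% test for temporary interruption. Under the primary estimand, data within the timeframe of that event are discarded (SAP 4.2.2.1), so a woman placed on the wrong side of 80% loses her Week 12 WASO.

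The version history of the SAP says the rule was added after blinded data review. It was therefore written in response to the data, although the documents do not say how many women it affects.

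**Working it through.** **Inputs**
- Capsules per treated night: 2 (Protocol 6.1, 6.6).
- D = days from first intake to the last Week 12 PSG night, inclusive. I use D = 86, the SAP's own stand-in day when that PSG is missing (SAP 6.4.2).
- Compliance = 100 × capsules taken / (2 × D) (SAP 6.4.2).
- Interruption threshold: below 80%.

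**1. The plan's figure.** The SAP credits 1 capsule. Its own inputs, a treated night at a fixed two-capsule dose, give 2. The figure of 1 does not follow from them.

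**2. Size of the understatement.** If two capsules were taken, compliance is low by 1/(2D). At D = 86 that is 1/172 = 0.58 percentage points. It runs from 0.60 points at D = 84 to 0.49 at D = 103, the last day of the SAP's Week 12 mapping window (SAP 4.2.1). A woman who took every dose scores 171/172 = 99.42% instead of 100%.

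**3. Where the 80% result changes.** At D = 86, 80% of 172 is 137.6 capsules. Take a woman with 136 capsules recorded before the last night:

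| Credit for last night | Capsules | Compliance | Below 80%? |
|---|---|---|---|
| 0 (no imputation) | 136 | 79.07% | yes |
| 1 (SAP rule) | 137 | 79.65% | yes |
| 2 (planned dose) | 138 | 80.23% | no |

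The 136 capsules equal 68 full doses in 85 nights, so whole-dose intake can reach this point.

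**4. How narrow the edge is.** With c capsules before the last night, the result changes only if c + 1 < 1.6 × D ≤ c + 2. Exactly one whole number satisfies this for each D:

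| D | Planned | Prior count that flips | With 1 | With 2 |
|---|---|---|---|---|
| 85 | 170 | 134 | 79.41% | 80.00% |
| 86 | 172 | 136 | 79.65% | 80.23% |
| 87 | 174 | 138 | 79.89% | 80.46% |
| 90 | 180 | 142 | 79.44% | 80.00% |

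She must also have at least 5 intake days in the last 7. Otherwise the other criterion makes her an interruption case whatever is imputed. That criterion is unaffected by the choice, because one capsule already counts as a day with intake.

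**5. Which analyses see it.** Week 12 WASO is a secondary endpoint, analysed in the same MMRM as the primary (SAP 4.3.1.1). For a woman who completes Week 12, her Week 4 flag and Week 4 value do not change. The first supplementary estimand, sleep efficiency, PROMIS and ISI use treatment policy for interruption and keep her data (SAP 4.2.3.1, 4.3.1.2, 4.3.2).

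**The case against.** The best defence is that 1 is a deliberate minimum. The SAP says the eCRF indicates that treatment was taken; it does not say that this page gives a capsule count for that night. One capsule is the least that fits the confirmed fact, and it matches the SAP's definition of a day with intake. It stands that the eCRF, as described, does not prove two capsules. But the SAP does not state this rationale, and the logic suits only the criterion that counts days. The percentage formula counts capsules against two per day, and there a confirmed night should carry the planned dose unless something indicates otherwise.

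Three other points on this side stand:
- A reader might infer that the rule penalises women. Compared with leaving the night empty, it raises compliance (79.07% to 79.65% in the example). SAP 4.1.1.3 otherwise imputes no missing ePRO assessments. The shortfall is relative to the planned dose only.
- SAP 4.5.1 also presents compliance from the eCRF pages, so the diary summary has a cross-check. At full adherence, 99.4% stays in the 80 to 120% category.
- A change of status needs the missing form, the eCRF confirmation, the single critical count and the 5-of-7 condition all together, among about 78 randomized women. The documents do not show that anyone is at that point.

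**Conclusion.** The rule is inconsistent with the fixed dose and with its own denominator, and the effect is small. Diary compliance is understated by one capsule, 0.58 points at day 86, for an affected woman who took both capsules. In a one-count edge case this costs her Week 12 WASO value under the primary-estimand handling.

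This rests on two assumptions: that a night the eCRF confirms as treated normally means the full two capsules, and, for the worked figures, that the last PSG night is day 86.

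A reader might go further and infer that the primary Week 4 result is compromised. The documents do not support that. The rule concerns the Week 12/EoT night, and discarding a Week 12 value can move the Week 4 estimate only indirectly, through the jointly fitted MMRM. No hypothesis is tested (SAP section 2), so no test decision is at stake.

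**What to change.** In SAP 4.5.1 and 6.4.2, impute the planned 2 capsules when the eCRF confirms intake on that night. Do not add an exception based on the Drug Accountability count: it is a cumulative total, and a shortfall in it cannot be assigned to one particular night. Before unblinding, at the review of intercurrent events already planned in SAP 4.1.3, list any participant whose status depends on 1 versus 2.

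The cost is one number in two SAP sentences and in the derivation program, plus a short listing. The change has a small downside: for a woman who took only one capsule that night, compliance would be overstated by one capsule. This concerns data derivation only and leaves dosing as it is.
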